NCT02848599

ID: 25-1:6563-3/2014

The Influence of
Postoperative Analgesia
on Systemic Inflammatory
Response and POCD
After Femoral Fractures
Surgery

Document Date: May 26, 2017

Category data were represented by absolute and relative frequencies. Variations of category variables were tested by Fisher's exact test. The numerical data are described by the median and the limits of the interquartile range. The normality of distribution of observed numeric variables was tested by the Shapiro -Wilk test. The differences between the normal distribution of numeric variables between the two independent groups were tested by Mann-Whitney's In Test. To determine the difference between the two dependent samples, Friedman's test was used. Logistic regression was used to assess the influence of several factors on the likelihood that POCD would develop in the observed subjects. The receiver operating curve (ROC) analysis was used to determine the optimal threshold, area under the curve (AUC), specificity, and sensitivity of the tested parameters. All P values were two-tailed. The level of significance was set at Alpha = 0.05. The statistical analysis was performed using MedCalc Statistical Software version 14.12.0 (MedCalc Software bvba, Ostend, Belgium; <http://www.medcalc.org>; 2014)

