NCT02848599

ID: 25-1:6563-3/2014

Document Date: May 26, 2017

The Influence of  
Postoperative Analgesia  
on Systemic Inflammatory  
Response and POCD  
After Femoral Fractures  
Surgery

The study was approved by the University Hospital Osijek Ethics Committee (Approval number 25-1:6563-3/2014, 19.5.2014.) and written informed consent was obtained from all subjects. The study design was a prospective, randomized, controlled trial. All patients received spinal anesthesia and one of two techniques of postoperative analgesia: intravenous patient-controlled analgesia (PCA) with morphine or patient-controlled epidural analgesia (PCEA) with 0.125% levobupivacaine. According to technique of postoperative analgesia which was applied, patients were allocated into two groups, the morphine group and the levobupivacaine group. Randomization was done before surgery by pulling out the envelope in which it was written the group division. Inclusion criteria were age  $\geq$  65, American Society of Anesthesiologists (ASA) physical status I-III, Mini-Mental State Examination (MMSE) score  $\geq$  17. Exclusion criteria were age  $<$  65, ASA physical status > III, MMSE score  $<$  17, history of dementia, schizophrenia, Parkinson's disease and cerebrovascular disease, use of opioids and benzodiazepines longer than one month before surgery, alcoholism, severe liver disease (class C according to Child-Pugh classification), severe kidney disease requiring hemodialysis, multiple trauma and the presence of head injury, communication issues such as serious hearing or visual impairment, any contraindication for regional anesthesia and for the both techniques of postoperative analgesia. Cefazolin 1g was given to all patients 30 minutes before incision and two other doses were given postoperatively. All patients were sedated with midazolam, 2 to 3 mg intravenously, before induction of anesthesia. In the morphine group spinal anesthesia was induced with subarachnoidally injection of 12.5-15 mg 0.5% levobupivacaine. In the levobupivacaine group combined spinal-epidural anesthesia was performed. First, the epidural space was entered with Tuohy epidural needle and the spinal needle was introduced via the lumen of the epidural needle into the subarachnoid space through which 12.5-15 mg of 0.5% levobupivacaine was injected. After that epidural catheter was inserted in the epidural space and its position was checked radiologically and confirmed with the test dose of 0.5% levobupivacaine after the spinal anesthesia was released. During the operation blood pressure was measured non-invasively every 5 minutes and its decrease greater than 20% from preoperative values was corrected by fluid administration and incremental IV injections of vasoconstrictors. The ECG and peripheral oxygen saturation by pulse oximeter were continuously monitored. Postoperative analgesia was obtained using patient-controlled analgesia (PCA) for the first 72 h. In the morphine group intravenous PCA was provided with the following settings: 0.5-2 mg/h basal flow, 0.5 mg bolus dose, and a 20-min lockout. Postoperative epidural PCA analgesia was obtained with 0.125% levobupivacaine with 6-12 ml/h basal flow, 2 ml bolus dose, and a 20-min lockout. Analgesia was assessed by Numerical Rating Scale (NRS), from 0 (no pain) to 10 (maximum pain) every three hours 72h postoperatively and then 3 times a day until discharge. In all patients complete blood count, differential blood count, CRP and fibrinogen were calculated 30 min before induction of anesthesia, 24h, 72h and 120h postoperatively. Blood glucose level was measured every 4 hours for 72h after

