
surgery and further depending on the values. The plasma concentrations of IL-6 was measured 30 min before induction of anesthesia, 24h and 72h postoperatively. Duration of surgery, blood loss, erythrocyte transfusion, body temperature and postoperative hospital stay were recorded. Cognitive functions were assessed using Mini-Mental State Examination (MMSE) preoperatively (baseline) and from the 1st to the 5th postoperative day and on the day of discharge (the day of surgery was marked as 0 day), once a day between 6 and 8 am. Anxiety and depression were assessed using Hospital Anxiety and Depression Scale (HADS) preoperatively (baseline) and on the 1st and 5th postoperative day and on the day of discharge once a day, at the same time when cognitive functions were evaluated.

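### Numeric outcomes are compared only by an unadjusted Mann-Whitney test, although preoperative IL-6, CRP, fibrinogen, blood counts, MMSE and HADS are collected and could serve as covariates

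*SAP*

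**What the plan says.** The SAP is a single paragraph. Its only between-group test for numeric variables is in this sentence: "The differences between the normal distribution of numeric variables between the two independent groups were tested by Mann-Whitney's In Test". The wording is garbled, since it pairs normality with a rank test, but on any reading the named test takes no covariate. Friedman's test is assigned to dependent samples and has no treatment term; if it includes the preoperative value, it does so only within patients. The one multivariable model, logistic regression, is for the binary outcome POCD. Neither document defines a change from baseline.

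The protocol schedules the covariates. For the routine laboratory markers: "complete blood count, differential blood count, CRP and fibrinogen were calculated 30 min before induction of anesthesia, 24h, 72h and 120h postoperatively". For IL-6: "The plasma concentrations of IL-6 was measured 30 min before induction of anesthesia, 24h and 72h postoperatively". MMSE is assessed before surgery, daily on days 1 to 5 and at discharge; HADS before surgery, on days 1 and 5 and at discharge. The protocol itself calls both preoperative assessments the baseline.

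Other numeric variables have no scheduled preoperative value: pain NRS, glucose, and the items in this sentence: "Duration of surgery, blood loss, erythrocyte transfusion, body temperature and postoperative hospital stay were recorded". They are outside this point, and so is POCD.

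**The concern.** The markers and scales with a preoperative value cover both themes of the trial's title, inflammation and cognition. A patient's postoperative value partly reflects where that patient started. An unadjusted comparison leaves that variation in the noise; a baseline covariate removes the predictable part of it.

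Two things are at stake. The first is power: a real difference between the two analgesia techniques is more easily missed. The second is chance imbalance: if the groups differ at baseline, part of that difference passes into the unadjusted comparison. Overall type I error is not at stake.

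**Working it through.** **Inputs.** From the SAP: two-sided testing at 0.05. From the protocol: two groups, and the schedules above. The documents give no sample size, effect size, SD, distribution or baseline-outcome correlation r, so there is no planned figure to reproduce. Assumed here: 40 per arm (also 30 and 60), an effect of 0.5 SD, and r = 0.1, 0.3, 0.5, 0.7.

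**Large-sample formula.** Adjusting for baseline multiplies the variance of the group difference by 1 − r². The standard error ratio is √(1 − r²); at r = 0.5 this is √0.75 = 0.87. The equivalent saving in patients is r²: 1, 9, 25 and 49%. The simulated ratios of the ANCOVA to the unadjusted standard error were 1.00, 0.96, 0.87 and 0.72.

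**Power by simulation** (normal data, 40 per arm, 20,000 runs per cell; Monte Carlo standard error about √(0.57 × 0.43 / 20,000) = 0.35 points). Mann-Whitney is applied to postoperative values.

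| r | Mann-Whitney | Rank ANCOVA | Gain | t-test | ANCOVA | Gain |
|---|---|---|---|---|---|---|
| 0.1 | 57.1% | 57.3% | 0.2 | 59.2% | 58.9% | −0.3 |
| 0.3 | 57.5% | 61.2% | 3.7 | 60.3% | 63.9% | 3.6 |
| 0.5 | 56.8% | 68.2% | 11.4 | 59.4% | 71.4% | 12.0 |
| 0.7 | 57.5% | 82.7% | 25.2 | 60.0% | 86.5% | 26.5 |

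Each gain compares like with like, so a change of test is not credited to the baseline.

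**Other sample sizes.** At 30 per arm Mann-Whitney has 45% at every r, and rank ANCOVA 45, 49, 55 and 70%. At 60 per arm the figures are 76% against 76, 79, 86 and 95%.

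**Other distributions** (40 per arm; r = 0.1, 0.3, 0.5, 0.7).

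| Data | Mann-Whitney | Adjusted |
|---|---|---|
| MMSE-like (latent mean 25, SD 3, rounded, capped at 30, baseline floor 17; 1.5-point effect) | 57/58/58/57% | rank ANCOVA 58/61/69/83% |
| Skewed marker, log SD 1 | 57/57/57/58% | log ANCOVA 60/63/72/87%; untransformed 42/44/49/62% |
| Symmetric marker, CV 0.25 | 58/57/58/57% | log ANCOVA 58/61/70/84%; untransformed 60/63/72/87% |

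The log scale therefore costs at most about 2 points when it was not needed (1.6 to 2.3), whereas ANCOVA without the log on a skewed marker can fall below Mann-Whitney.

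**Type I error.** Under the null, Mann-Whitney rejected in 4.5–5.2% of runs, ANCOVA in 4.8–5.3% and rank ANCOVA in 4.7–5.4%. All are sound overall.

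**Conditional on the observed baseline difference.** Let z be the standardised baseline difference between groups. Under the null the unadjusted statistic is then approximately normal with mean rz and variance 1 − r², so it rejects with probability Φ((−1.96 − rz)/√(1 − r²)) + 1 − Φ((1.96 − rz)/√(1 − r²)). At r = 0.5 and z = 2 the upper tail starts at (1.96 − 1)/0.866 = 1.11, and the two tails together give 13.4%. Simulated Mann-Whitney rejection, with the formula in brackets:

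| r | z = 0 | z = 1 | z = 2 |
|---|---|---|---|
| 0.1 | 5.1% (4.9) | 4.9% (5.0) | 5.1% (5.3) |
| 0.3 | 4.0% (4.0) | 4.9% (5.0) | 7.6% (8.1) |
| 0.5 | 2.5% (2.4) | 4.8% (4.8) | 12.3% (13.4) |
| 0.7 | 0.7% (0.6) | 3.7% (3.9) | 19.9% (21.6) |

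ANCOVA and rank ANCOVA stay at about 5% throughout. An imbalance of |z| ≥ 2 has probability 2(1 − Φ(2)) = 4.6% for any one variable.

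**The case against.** The strongest reply is that nothing here is wrong. Mann-Whitney is a legitimate test in a randomised trial, its error rate is sound and it contradicts nothing in the protocol. That stands: this is an improvement, not a correction.

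It is also fair that the size of the gain is assumed. Nothing in the documents places IL-6, CRP, fibrinogen, MMSE or HADS on the range of r, surgery comes between the baseline and every later value, and the outcomes may differ from one another. This limits what can be claimed about size, but not the direction.

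The SAP does not say whether Mann-Whitney compares values or changes. Values is the natural reading, since no change score is defined. On changes the variance is 2(1 − r) times that of a value, which is an improvement only when r exceeds 0.5. Simulated power for Mann-Whitney on change (40 per arm, 8,000 runs) was 36, 44, 58 and 79%, and a second run gave 35, 44, 57 and 80%. Against rank ANCOVA at 57, 61, 68 and 83% the gap becomes about 21, 17, 10 and 4 points. The pattern across r changes, but rank ANCOVA is ahead at every r on either reading.

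Finally, both documents are in the past tense and dated May 2017, three years after ethics approval. If the analysis was complete, prespecification is no longer possible. That reduces the benefit without removing it, because readers could still see whether the group differences survive adjustment.

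**Conclusion.** The point holds. For IL-6, CRP, fibrinogen, blood counts, MMSE and HADS, the SAP leaves scheduled preoperative data out of the comparison of the randomised groups. Under the stated assumptions the cost is close to nothing at r = 0.1, about 4 points of power at r = 0.3, 11–12 at r = 0.5 and 25–27 at r = 0.7. Adjustment also keeps the error rate near 5% when the groups differ by chance at baseline. In the cases tried, neither rank ANCOVA nor log-scale ANCOVA had lower power than Mann-Whitney on values. The change is worth making, but the existing analysis is not invalid. Confidence in the size is moderate, because sample size, effect, r and distributions are all assumed.

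**What to change.** Keep the Mann-Whitney sentence for all numeric variables not listed below, and state that it compares values. Then add:

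> For IL-6 (24 and 72 hours), CRP, fibrinogen and blood counts (24, 72 and 120 hours), MMSE (days 1–5 and discharge) and HADS (days 1 and 5 and discharge), the randomised groups are compared at each postoperative time point with the preoperative value as covariate. Laboratory markers are analysed by ANCOVA on the log scale, fixed before any group comparison, reporting the adjusted ratio with 95% CI; a marker that takes zero values is analysed by rank ANCOVA. MMSE and HADS are analysed by rank ANCOVA, for the P value. Unadjusted Mann-Whitney on values is a sensitivity analysis for these outcomes.

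Which markers fall under the zero-value rule should be settled without sight of group labels. Rank ANCOVA gives no effect estimate on the original scale. If a Hodges-Lehmann difference with CI is shown for MMSE or HADS, label it unadjusted and pair it with Mann-Whitney: the two tests' verdicts differed in about 9, 17 and 29% of MMSE-like runs at r = 0.3, 0.5 and 0.7.

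The cost is a few sentences of SAP text and some analysis time, with no new data. The number of main comparisons is the same as for Mann-Whitney at the same time points. Before blood counts it is 2 (IL-6) + 3 (CRP) + 3 (fibrinogen) + 6 (MMSE) + 3 (HADS) = 17, or 20 if HADS anxiety and depression are scored separately. If the analysis was complete when the SAP was dated, present the adjusted results as a labelled post hoc supplement beside the Mann-Whitney results.

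### Friedman's test is described for two dependent samples although no scheduled outcome has two readings, it cannot compare the analgesia groups, and the only between-arm test for numeric outcomes makes no stated use of the preoperative values already collected

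*SAP*

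**What the plan says.** The SAP is a single paragraph. On repeated readings it says only: "To determine the difference between the two dependent samples, Friedman's test was used". On the comparison of arms for numeric variables it says: "The differences between the normal distribution of numeric variables between the two independent groups were tested by Mann-Whitney's In Test". It does not say which visits that test covers, whether it uses raw values or changes, or whether Friedman's test is run pooled or by arm. Other sentences name Fisher's exact test for categorical data and logistic regression for the probability of POCD.

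The protocol sets these schedules:
- Laboratory markers: "complete blood count, differential blood count, CRP and fibrinogen were calculated 30 min before induction of anesthesia, 24h, 72h and 120h postoperatively".
- IL-6: "The plasma concentrations of IL-6 was measured 30 min before induction of anesthesia, 24h and 72h postoperatively".
- Cognition: "Cognitive functions were assessed using Mini-Mental State Examination (MMSE) preoperatively (baseline"), then daily on days 1 to 5 and at discharge.
- Anxiety and depression: "Anxiety and depression were assessed using Hospital Anxiety and Depression Scale (HADS) preoperatively (baseline"), then on days 1 and 5 and at discharge.
- Pain: "Analgesia was assessed by Numerical Rating Scale (NRS), from 0 (no pain) to 10 (maximum pain) every three hours 72h postoperatively", then three times daily to discharge.
- Glucose: every 4 hours for 72 hours.

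No preoperative reading is stated for pain or glucose. Body temperature is recorded, but the number of readings is not given.

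**The concern.** The trial is a randomised comparison of two analgesic techniques, and its title asks what analgesia does to the inflammatory response and to POCD. A significant Friedman result shows that a marker moved after surgery, which is expected in both arms. If it is reported beside the arm results, within-arm change may be taken for a treatment effect.

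For numeric outcomes the treatment question falls to Mann-Whitney alone. Six outcomes or outcome groups have a preoperative value, and the SAP does not say that any of these values enters the comparison of arms. Precision is given up on data already collected. With visit and scale left open, the test could be repeated at every visit, or the visit chosen after the results are known.

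**Working it through.** **1. Count the readings (protocol schedules).**

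| Outcome | Preoperative | Postoperative | Total |
|---|---|---|---|
| IL-6 | 1 | 2 | 3 |
| CRP, fibrinogen, blood counts | 1 | 3 | 4 |
| HADS | 1 | 2 fixed + discharge | 4 |
| MMSE | 1 | 5 fixed + discharge | up to 7 |
| Glucose, first 72 h | none stated | 72/4 = 18 | about 18 |
| NRS, first 72 h | none stated | 72/3 = 24 | about 24 |

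None has two readings.

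**2. What Friedman's test can show.** With n patients and k readings, Q = 12n/[k(k+1)] × Σ(R̄_j − (k+1)/2)². At k = 2 this reduces to the sign test. If 20 of 30 patients rise, Q = 4 × 30 × (20/30 − 1/2)² = 3.33, and the sign-test z² = (20 − 15)²/7.5 = 3.33. With three or more readings it is a valid test of change over time. Ranks are taken within each patient, so adding 5 units to every reading in a simulated arm left Q at 63.05. A constant difference between arms is invisible to it.

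**3. What baseline adjustment is worth.** The documents give no sample size, SD, effect or correlation, so there is no stated figure to reproduce. Assumptions: 30 per arm, normal data, effect d = 0.5 SD at the visit, two-sided alpha 0.05 (from the SAP), and correlation r = 0.3/0.5/0.7 between readings. Power ≈ Φ(z − 1.96), with z = d√(n/2)/√v and √(30/2) = 3.873.

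- Mann-Whitney at one visit, raw values (efficiency 3/π = 0.955 for normal data): z = 0.5 × 3.873 × √0.955 = 1.892, power about 47%. Simulation (4,000 runs): 45/44/44%.
- Baseline-adjusted (ANCOVA) at one visit: v = 1 − r² = 0.91/0.75/0.51, z = 2.03/2.24/2.71, power about 53/61/77%. Simulation: about 50/58/76%.

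The hand formula runs a little high because it ignores the t distribution. Where there is an effect at the visit, the gain there does not depend on what happens at other visits.

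**4. Averaging three postoperative readings (ANCOVA on the mean).** With equal correlation, v = (1 + 2r)/3 − r² = 0.443/0.417/0.310.

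- Sustained effect, 0.5 SD at all three times: z = 2.91/3.00/3.48, power about 83/85/94%; simulation 81/82/92%.
- Effect at the first visit only, mean effect 0.5/3 = 0.167 SD: z = 0.97/1.00/1.16, power about 16/17/21%; simulation 16/15/21%.
- Waning effect (0.5, 0.33, 0.17 SD; mean 0.333 SD), equal correlation: z = 1.94/2.00/2.32, power about 49/52/64%; simulation 47/51/60%.
- The same waning effect with first-order autoregressive correlation: v = [3 + 2(2r + r²)]/9 − [(r + r² + r³)/3]² = 0.467/0.526/0.492, z = 1.89/1.78/1.84, power about 47/43/45%; simulation about 40 to 45%. First-visit Mann-Whitney has about 45%, so there is no gain.

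**5. Repeated single-visit testing.** If unadjusted Mann-Whitney were run at every fixed visit with no arm difference, at least one P < 0.05 would occur in about 8–10% (2 visits), 10–14% (3) or 13–23% (5). Independent tests would give 1 − 0.95² = 9.8%, 1 − 0.95³ = 14.3% and 1 − 0.95⁵ = 22.6%. The SAP does not say the test is used this way.

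**The case against.** The Friedman sentence is close to a slip of the pen. The Mann-Whitney sentence is loosely worded too, and replacing two by three or more would cure the description. That stands: the wording alone is minor.

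Mann-Whitney at a visit is valid in a randomised trial, and omitting the baseline does not bias it. That also stands. A reader might infer that the arms are never compared, or that the unadjusted comparison is wrong. The SAP does name a between-arm test, and what it loses is precision.

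A reader might also infer that the plan cannot test an effect of analgesia on POCD. The documents do not support this: Fisher's exact test and logistic regression are named and can address binary POCD.

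It could be said that one sentence fixing the visit and using change scores would suffice within the rank approach. In part it would. But in the simulation above, one-visit Mann-Whitney on change has 34/46/66% power against about 50/58/76% with baseline adjustment, and at r = 0.3 it does worse than raw values.

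The most tempting overreach is to read the 81/82/92% for the average as the cost of the present plan. It requires an effect sustained over all three readings. The documents say nothing about its time course, and under other patterns averaging gains nothing or loses.

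Finally, the SAP summarises numeric data by medians and quartiles, so the normal-data figures are only a guide. With a sustained effect, a rank version of the baseline-adjusted average gave 78/80/88%, so the gain in that setting does not depend on the normal model.

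**Conclusion.** The point holds and should be fixed, but it is not fatal. Two things follow from the documents without any assumption. The description of Friedman's test fits no outcome with a stated schedule, and that test cannot carry a between-arm conclusion. The between-arm test for numeric outcomes makes no stated use of baselines collected for IL-6, CRP, fibrinogen, blood counts, MMSE and HADS.

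The size is illustrative. Adjustment at a single visit adds roughly 5 to 30 percentage points of power as r goes from 0.3 to 0.7. Whether to average over visits is a judgement for the sponsor. NRS and glucose are excluded for want of a stated preoperative value, and body temperature cannot be judged because its schedule is not given.

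**What to change.** 1. Reword the Friedman sentence to refer to three or more dependent readings. State that Friedman's test and all within-arm tests are descriptive and that no conclusion about the groups is drawn from them.

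2. For IL-6, CRP, fibrinogen, blood counts, MMSE and HADS, compare the arms at each fixed postoperative time with the preoperative value as covariate. Use ANCOVA, or a mixed model with group, time, group-by-time and baseline. Log-transform IL-6 and CRP. For MMSE and HADS a baseline-adjusted rank analysis may be used instead; say in advance which method applies to which outcome.

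3. For each outcome name one lead contrast, either a single fixed time or the average over the fixed times. Treat the other times as secondary. Keep Mann-Whitney as supportive, with its visits and scale listed.

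4. Analyse discharge-day MMSE and HADS separately, adjusted for baseline, because the day of discharge can differ between patients.

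5. Both documents are in the past tense. If the data have already been analysed, label the change post hoc.

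The cost is SAP wording and modest extra analysis, possibly in software other than the package named. No new data are needed. An average dilutes an effect confined to one visit, which is why the per-time contrasts are kept. Naming one lead contrast per outcome does not settle multiplicity across the outcomes.

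### The only multivariable cognitive analysis is on POCD yes/no; a baseline-adjusted regression of the MMSE score should be added beside it

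*SAP*

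**What the plan says.** The protocol's closing passage on assessments names a single cognitive instrument: "Cognitive functions were assessed using Mini-Mental State Examination (MMSE) preoperatively (baseline) and from the" first to the fifth postoperative day, and again at discharge. HADS is also recorded, but it measures anxiety and depression. Neither document defines POCD: there is no MMSE fall, threshold or time point.

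The SAP is one paragraph. Its only model with several factors is the POCD model: "Logistic regression was used to assess the influence of several factors on the likelihood that POCD would develop in the observed subjects". The factors are not listed. For numeric variables, differences "between the two independent groups were tested by Mann-Whitney's In Test". For repeated readings, "To determine the difference between the two dependent samples, Friedman's test was used". Categorical variables are covered by "Variations of category variables were tested by Fisher's exact test". The paragraph also plans ROC analysis. It names no regression on the MMSE score or its change.

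**The concern.** If POCD is a cut of the MMSE, a patient who falls just past the cut counts the same as one who falls far past it, and a patient one point short counts as unchanged. When decline is graded, that costs power and precision.

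The other tests named do not fill the gap. Mann-Whitney can compare MMSE scores between arms, but it takes no covariates. Friedman compares readings within patients and takes none either. Entry allows any baseline MMSE of 17 or more, so patients can start far apart, and baseline is an obvious adjustment variable that is already measured. As the SAP stands, any adjusted statement about how analgesia or another factor relates to cognition can come only from the yes/no scale, with a threshold the documents do not state. A real but graded effect is then more likely to be reported as absent.

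**Working it through.** The plan has no sample size or power figure to reproduce. The only usable input it gives is the test level: "The level of significance was set at Alpha = 0.05" and "All P values were two-tailed".

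**Assumptions (not in the documents).** Equal allocation with 30 or 60 per arm; MMSE SD 3; correlation 0.6 with baseline; a uniform arm shift of 0.5 SD = 1.5 points; POCD as a cut on MMSE fall.

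**Standard deviations.**
- Residual SD after baseline adjustment: 3 × √(1 − 0.6²) = 2.4.
- SD of the change score: 3 × √(2 × (1 − 0.6)) = 2.68.

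**Power formula.** Power ≈ Φ(δ/σ × √(n/2) × √e − 1.96), where e is the efficiency of the method. For the full score e = 1. For Mann-Whitney under normality e = 3/π = 0.955. For a cut giving POCD proportion p, e = φ(z_p)²/(p(1 − p)) = 0.64, 0.58, 0.49 and 0.34 at p = 50%, 30%, 20% and 10%.

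**Numbers in, 30 per arm (√(n/2) = 3.873).**
- Baseline-adjusted score: 1.5/2.4 × 3.873 = 2.42; Φ(0.46) = 68%.
- Yes/no, adjusted, p = 50%: 2.42 × √0.64 = 1.93; Φ(−0.03) = 49%. At p = 20%: 2.42 × √0.49 = 1.69; Φ(−0.27) = 39%.
- Mann-Whitney on change: 1.5/2.68 × 3.873 × √0.955 = 2.12; Φ(0.16) = 56%.
- Mann-Whitney on raw postoperative score: 1.5/3 × 3.873 × √0.955 = 1.89; Φ(−0.07) = 47%.

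At 60 per arm (√(n/2) = 5.477) the same steps give 93%, 78% to 67%, 85% and 76%.

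**Simulation.** Integer MMSE capped at 30, baseline mean 25, mean fall of 1.5 points in the reference arm, and POCD as a fall of at least 2, 3, 4 or 5 points (20 to 62% POCD overall). Both models were adjusted for baseline.

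| Per arm | Logistic on POCD, cut 2/3/4/5 | Linear on MMSE | Difference, points |
|---|---|---|---|
| 30 | 46/47/45/37% | 67/65/64/64% | 21/18/19/27 |
| 60 | 73/75/69/61% | 92/92/92/91% | 19/17/23/30 |

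A second run gave 36 to 43% against 63 to 66% at 30 per arm, and 63 to 78% against 91 to 92% at 60. Taken together, the loss is roughly 15 to 30 points. In that run Mann-Whitney on change scores had 53 to 56% and 84 to 86% power, roughly 5 to 12 points below the adjusted regression. On raw scores it had 46 to 49% and 76%, which is no better than the better yes/no cuts. In the first run, with no effect, the linear model rejected in 4.1 to 5.6% of trials, so its gain is not bought with false positives.

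**Where the loss shrinks.**
- Shift of 0.2 SD (0.6 points): the formula gives 16% against 10 to 12% at 30 per arm and 28% against 16 to 19% at 60, a loss of about 4 to 12 points. Simulation gave 3 to 12.
- Shift of 1.0 SD (3 points): 99.8% against 92 to 97% at 30 per arm, and no material loss at 60. Simulation gave 0 to 7.
- Decline confined to a subset, 50 per arm, 30% against 10% declining, cut at half the fall, unadjusted. If decliners fall by 4 noise SDs, the mean comparison has Φ(0.8/√((4.36 + 2.44)/50) − 1.96) = 58% power. The yes/no comparison (30.9% against 11.8% past the cut) has 65%, so yes/no wins by about 6 points. If decliners fall by 2 noise SDs, the figures are 35% and 32%, so yes/no loses about 3.

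**Where it grows.** With POCD near 10%, simulated regressions at full-score powers of about 50 to 90% lost 27 to 48 points.

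**The case against.** The strongest objection is that any figure for lost power belongs to the assumptions and not to this trial. That stands. The documents fix neither the sample size, the effect, the MMSE spread nor the POCD rate, and a uniform shift is the pattern that most favours the full score. An outcome described as developing POCD may suggest that a distinct subset declines, and there the yes/no analysis can do slightly better.

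Second, the randomised arm comparison is valid without covariates, and the SAP's Mann-Whitney test already permits it on the graded score. That also stands. A reader might infer that the plan discards graded decline altogether; it does not. The graded score is missing only from the factor model. What remains is the efficiency lost by ignoring baseline, and the SAP does not say whether raw or change scores would be tested.

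Third, POCD is the outcome in the title and in the SAP's model, and a difference in MMSE points answers a related but different question. This is a fair reason not to demote the POCD analysis. It is no reason against adding a model beside it.

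Fourth, the calculations concern the arm effect. The SAP's factors are unnamed, so arm may not be among them, and no inflammatory marker was simulated. The proportional-odds model was not run either; regression on ranks stood in for it, with 61 to 63% power at 30 per arm and 89 to 91% at 60. The size of any loss for other factors is therefore not established.

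**Conclusion.** The concern holds in a limited form. The only multivariable cognitive analysis is on POCD yes/no, and no baseline-adjusted analysis of the MMSE score is planned. That POCD is an MMSE cut is an inference from the absence of any other cognitive test.

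Under a uniform 0.5 SD shift, 30 to 60 per arm and POCD of about 20 to 62%, the yes/no model gives up roughly 15 to 30 points of power for the arm effect. Away from those conditions the loss can be near zero, reversed or, when POCD is rare, larger.

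A reader might go further and attach one fixed loss of power, or a fixed share of discarded information, to this trial. The documents do not support that: the efficiency of a cut depends on a POCD rate they do not give, and it assumes a normal shift. The recommendation rests on the direction of the loss under graded decline and on the low cost of the remedy. It is an analysis that should be added; the existing one is not invalid.

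**What to change.** In the SAP, keep the logistic regression on POCD and state the MMSE cut-off and the time point that define POCD. Beside it, add a prespecified linear or proportional-odds regression of postoperative MMSE, at one fixed reading or as the mean of a fixed set of days, on arm, baseline MMSE and the same preoperative factors. List those factors. Report the adjusted arm difference in MMSE points, or the common odds ratio, with a 95% CI.

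Both documents are written in the past tense. If outcome data by arm have already been examined, the added model should be labelled as such.

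The cost is SAP wording and one extra model on data already collected. The downsides are small: MMSE points or a common odds ratio are less familiar clinically than a POCD rate, which is still reported; the ceiling at 30 favours the ordinal form; and the ordinal model may need software other than the package named.
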